### **Outcome Measures:**

**BMI and baseline blood samples will be obtained at the screening visit.** All other measures will be assessed at the baseline visit and at the end of the 4-week intervention period except for the following: 1) Actigraphy watch will be worn continuously, and daily sleep diary completed for the entire study period, 2) The sleep hygiene pre/post-test and safety pre/post-test (control group only) will be given prior to intervention, immediately post intervention and at end of 4-week intervention period (3 time points), 3) Participant characteristics questionnaire only at baseline, and 4) Both groups will receive the exit survey at end of 4 week intervention period. **Insulin Resistance:** A) Glucose and insulin levels will be measured from fasting serum samples. B) Insulin Resistance will be calculated from the measured glucose and insulin levels using standard formulas. Briefly, serum samples will be collected via venipuncture and analyzed at Cardiovascular Specialty Laboratories, Inc (Atlanta, GA) using standard laboratory approaches with calibrated equipment (See letters of cooperation, from [name] and [name]). These two values will be used to calculate the homeostatic model assessment of insulin resistance (HOMA-IR; blood glucose level X insulin level, divided by 22.5). Elevated values indicate IR. A cutoff score of HOMA-IR < 2.1 as normal and HOMA-IR  $\geq$  2.1 as elevated (evidence of IR) will be used as determined in non-diabetics (Esteghamati et al., 2010). **Sleep Duration:** Using wrist actigraphy (Motionlogger, AMI, Ardsley, NY) along with a sleep diary (required to help validate and score actigraphy data; Martin & Hakim, 2011), we will objectively monitor each participant's 24-hour sleep-wake cycle to obtain average sleep duration (total sleep time) for one week (baseline) prior to random assignment to group and will continue monitoring during the 4 week intervention period. All participants wear the device (looks like a watch) on the wrist continuously for a total of 5 weeks (1 week for baseline sleep and 4 weeks of intervention period), except while bathing or swimming. Leproult and colleagues (2015) had success with adults wearing a wrist actigraph continuously for a total of 8 weeks. This device contains a light sensor that stores activity counts in 1-minute epochs and will detect the onset and offset of sleep using concurrent data from sleep diaries (Buysse et al., 2008; Morgenthaler et al., 2007). The Motionlogger was successfully validated against polysomnography on dimensions of sleep patterns: sleep onset latency, wake time after sleep onset, total sleep time (sleep duration), and sleep efficiency percentage (Cole et al., 1992). Data for each sleep component will be averaged over the 7 days for each week of the protocol (e.g. average sleep efficiency percentage, average total sleep duration) for analysis. Actigraphy has been compared to polysomnography to detect sleep and wakefulness and found to have a sensitivity of .965 and accuracy of .863 (Marino et al., 2013). The sleep diary is necessary to record data to help interpret actigraphy data (time in bed, time awake, and anything that occurs during the night such as waking up in the middle of the night). Participants in the SLEEP-Extend group will also use a daily sleep diary to record any sleep hygiene practices they use. Participants in the control group will use the same daily sleep diary as the SLEEP-Extend group with the difference of recording any safety practices used rather than recording sleep hygiene practices used. **Sleep Hygiene Knowledge:** To assess

the fidelity of the intervention, we are including a sleep hygiene test that will be given at 3 time points: as a pre-test, and as a post-test immediately after the education and at the end of the 4-week intervention period. The researcher-developed sleep hygiene questionnaire is based on the sleep hygiene recommendations from the NSF and the American Academy of Sleep Medicine (AASM). Participants will identify true or false if an item is recommended to facilitate sleep. Non-sleep hygiene items will be included. In addition, the control group will receive an investigator-developed instrument with the list of safety practices based on safety information they receive. Both instruments will be reviewed for content validity by a content expert and researcher with measurement expertise. **Physical activity and Dietary characteristics:** Physical activity will be measured by activity levels from the actigraphy monitor as well as self-report using the Baecke questionnaire (Baecke, Burema & Frijters, 1982). Dietary habits will be measured by self-report using the 26-item Dietary Screener (National Cancer Institute, 2015). Both the Baecke questionnaire and Dietary Screener have evidence of validity (Philippaerts, Westerterp, & Lefevre 1999; Thompson et al, 2005). Diet and physical activity are also reported to impact IR, and a recent study found that in adolescent girls, poorer diet and lower physical activity were associated with higher levels of IR (Jiménez-Pavón et al, 2013). Measuring this at baseline and after the 4-week intervention period will allow us to assess if dietary and/or physical activity were mediators between sleep duration and IR. **Adherence to the intervention:** The percent of days extending time in bed will be computed from the total number of days TIB was actually extended by one hour over the total intervention days (4 weeks = 28 days). **Exit Interview:** Participants in both groups will be interviewed after the 4-week intervention period. This investigator-developed interview will assess their satisfaction with the intervention, any difficulties implementing the intervention strategies and what they felt was most effective and if they would recommend others to participate in the intervention. The interview questions will be reviewed by a content expert and researcher with measurement expertise. **Participant Characteristics:** Will be assessed at baseline via an investigator-developed questionnaire which will include T2DM risk factors based on the ADA risk assessment tool [male gender, family history of diabetes, high blood pressure, and physical inactivity (ADA, Are you at risk?)]. Additional data will include age, marital status, and factors that may affect sleep and/or glucose/insulin levels such as work hours, health problems, and medications. Calculation of BMI from height (stadiometer) and weight (calibrated scale) using a standard formula will be obtained. These data will describe the sample, and a total T2DM risk factor score will be calculated by summing the number of risk factors. Other data will be evaluated as potential covariates. BMI will be assessed at screening and at the end of the 4 week intervention period in both groups.

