receive \$20 after one week of baseline data. At the end of the study, all participants will receive an additional \$30, a certificate of appreciation and a booklet on Healthy Sleep (NHLBI, 2011). Any participants that are noted to have additional risk factors for T2DM will be provided educational material on reducing T2DM risk factors and the suggestion made to follow up with a physician. After serum blood values are analyzed, all participants will be sent a letter with their glucose, insulin and HOMA-IR information along with a description of these values and recommendation for physician follow up. The principal investigator is a registered nurse who will collect the data and administer the sleep intervention. Standard universal precautions will be used during blood draws. Additionally, a GRA, also a registered nurse, will assist with data collection.

**Sample size:** A target sample size of 10 in the SLEEP-Extend group and 10 in the control will be used for this feasibility study (accounting for 20% attrition) given the need for a serum blood test as part of screening a number of participants to meet strict eligibility criteria. Participants will be randomly assigned to either the control or SLEEP-Extend group using a table of random numbers.

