**Overview of the SLEEP-Extend Intervention:** The SLEEP-Extend intervention is comprised of two components that will be administered one week after baseline data are collected. The first component consists of aiming to increase sleep duration by increasing time in bed (TIB) by one hour total per night for 4 weeks. Increasing TIB has been a successful strategy used to extend sleep duration in multiple studies (Dewald-Kaufmann, Oort, & Meijer, 2013; Gumenyuk et al., 2011; Kamdar, et al., 2004; Leproult et al., 2015). We will determine with participants when TIB can be extended for one hour total per night (either going to bed earlier or staying in bed later) depending on their preference and instructing participants to increase TIB for one hour total each night for 4 weeks. The second component of the intervention consists of one educational session regarding using sleep hygiene strategies (routine for going to sleep). Healthy sleep hygiene includes strategies such as having a regular bedtime and wake time and avoidance of stimulating food/drink or activities before bedtime (AASM, *Healthy Sleep Habits*; NSF, *Sleep Hygiene*). Participants will use a daily sleep diary to record any sleep hygiene practices they use. The control group will only receive one educational session consisting of safety practices used for an urban environment. Control group participants will use a similar daily sleep diary to record any safety practices they use.

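### Sleep duration is scored with a diary whose content differs by arm, and the plan names no scorer, no masking and no rule for setting sleep intervals

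*Combined protocol and SAP*

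**What the plan says.** Under Outcome Measures, the diary is part of the measurement of sleep duration. It is "required to help validate and score actigraphy data", and the actigraph "will detect the onset and offset of sleep using concurrent data from sleep diaries".

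The same section makes the diary's content depend on the arm. On one side, "Participants in the SLEEP-Extend group will also use a daily sleep diary to record any sleep hygiene practices they use". On the other, the control diary is described as the same "with the difference of recording any safety practices used" in place of sleep hygiene practices. The overview of the SLEEP-Extend intervention repeats this: "Control group participants will use a similar daily sleep diary to record any safety practices they use".

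On staff, PROCEDURES states: "The principal investigator is a registered nurse who will collect the data and administer the sleep intervention". A graduate assistant, also a nurse, helps with data collection. Under Informed Consent Process and Visit Details, the actigraph and diary go back to the researcher at the last visit.

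That section also lists the diary fields when the diary is first issued, before randomization: time to bed, time of waking, and awakenings. It carries the diary forward for four more weeks by referring back to that list. It mentions no practice entries.

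The Analysis Plan expresses sleep as percent change from start to end. It calls for interrater reliability when exit interviews are coded, and for nothing comparable when actigraphy is scored. The documents do not mention masking, an independent scorer, removal of practice entries before scoring, or what to do when diary and actigraph disagree.

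**The concern.** Deciding where a night's sleep interval begins and ends can involve judgement, above all when the diary and the activity trace disagree. If the person deciding can see the arm, and also delivered the intervention, expectation may influence the decision. Minutes added at the edge of an interval need not be sleep to raise recorded sleep time, because actigraphy scores some quiet wake as sleep.

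The stake is the between-arm comparison of sleep duration in H1. The introduction makes extension of sleep part of the foundation for a larger study. With a target of 10 per arm, a modest systematic shift in one arm could affect that estimate, and nothing in the planned analysis would reveal it.

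**Working it through.** There is no planned figure to reproduce here, because the plan does not quantify scoring error. The check has three parts.

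**1. Can the scorer know the arm?**
- The diary is needed for scoring, and its practice entries differ by arm after randomization (Outcome Measures; overview of the intervention).
- The person who delivers the intervention also collects the data (PROCEDURES), and the diary returns to the researcher (Visit Details, final visit).
- No provision separates these roles or removes the entries.

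So the plan as written leaves the scorer likely to know the arm. It does not say who the scorer is.

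**2. Would a bias cancel against baseline?**
- Both visit schedules record the baseline week before randomization. Visit Details also uses that week's average sleep to decide eligibility, so it must be scored before an arm exists. PROCEDURES says only that the data are downloaded at the visit where randomization occurs.
- Let B be baseline sleep, F final sleep and b a scoring shift in the intervention weeks. Percent change is 100 × (F + b − B)/B = 100 × (F − B)/B + 100 × b/B.

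The term 100 × b/B remains. If b differs between arms, it enters the comparison directly.

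**3. How large could it be? (illustration only)**

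Inputs from Outcome Measures: "sensitivity of .965 and accuracy of .863". Specificity for wake is not given. With p the share of recorded time that is truly sleep (assumed):

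accuracy = p × sensitivity + (1 − p) × specificity, so specificity = (0.863 − 0.965p)/(1 − p).

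- p = 0.70: (0.863 − 0.6755)/0.30 = 0.625
- p = 0.80: (0.863 − 0.7720)/0.20 = 0.455
- p = 0.85: (0.863 − 0.82025)/0.15 = 0.285

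The formula needs p below 0.863/0.965 = 0.894; above that, specificity would be negative.

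Suppose intervals in one arm are widened by 30 minutes of wake per night (assumed). Apparent sleep gained is 30 × (1 − specificity):

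- p = 0.70: 30 × 0.375 = 11.3 min
- p = 0.80: 30 × 0.545 = 16.4 min
- p = 0.85: 30 × 0.715 = 21.5 min (21.45 before rounding)

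That is about 11, 16 and 21 minutes. Turning this into an error rate would need a standard deviation for sleep duration, which the plan does not give.

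**The case against.** The strongest reply is that the documents never say scoring is unmasked. They name who collects data, not who places rest intervals. This stands: the scorer's knowledge of the arm is an inference from who handles the material and from the absence of any masking provision.

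Second, a reader might infer that every diary page discloses the arm. The documents do not show that. Visit Details lists only timing fields, to be kept in a phone app or on paper, and continues that diary after randomization. Outcome Measures and the intervention overview do require practice entries, but not where on the form. The two descriptions need reconciling, and until then the extent of disclosure is unknown.

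Third, some protection is already there. Data carry unique numbers (Protection of Human Subjects), and sleep within the interval is judged from recorded activity, which limits what a scorer can add. But a number hides a name, not an arm, and the edges of the interval still depend on the diary.

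Fourth, the minutes above rest on an assumed widening and assumed sleep shares, and they move a good deal with the share. They also apply a whole-recording error rate to minutes at the edges, where movement may be more common and would be scored as wake. Setting them against the one-hour target would compare apparent sleep with time in bed. All of this stands.

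Finally, masked scoring would not address two other sources of error. Participants know their arm and report their own bed and wake times, and quiet wake during the added time in bed may be scored as sleep by anyone. This also stands, and it limits what the fix can achieve.

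**Conclusion.** The concern holds as a gap in the plan. Sleep duration in the four intervention weeks is open to arm-aware scoring: the diary used for scoring carries arm-specific entries, the interventionist collects the data, and neither masking nor an interval rule is stated. Any resulting bias would not cancel against baseline.

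Two stronger conclusions may be inferred but are not supported. One is that scoring is definitely unmasked; the scorer is not named. The other is that SLEEP-Extend sleep will be inflated by a known amount; neither direction nor size can be derived from the documents. The range of about 11 to 21 minutes per night is conditional on 30 minutes of added wake and a sleep share of 70% to 85%, all assumed.

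Nor should sleep duration be called the primary outcome: Aim 1 is feasibility and acceptability, and no outcome is labelled primary. The point is worth acting on because the remedy costs little.

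**What to change.** - Keep the timing diary identical in both arms, limited to the three fields already listed in Visit Details. Record sleep hygiene or safety practices on a separate log, and bring Outcome Measures, the intervention overview and Visit Details into line on this.
- Name the scorer. Have one existing team member prepare coded files without arm labels or practice entries, and the other score them where possible.
- Use the device's automatic algorithm, with a fixed written rule for setting rest intervals and for resolving disagreement between diary and actigraph. Write it before any intervention-week data are scored.
- State the remaining limitations: participants' reports of bed and wake times are unmasked, and quiet wake during the added time in bed may be scored as sleep.

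The cost is a reformatted diary and minor file handling, with no added participants, visits or devices. Only two staff are described, both collect data, and longer nights may themselves hint at the arm, so masking may be incomplete. In that case the fixed rule gives the main protection, and the report should say so.

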## **Objectives**

**Aims:** The aims for this pilot study of young adults ages 18-25 years old with IR (based on established cut points), short sleep (< 7 hours/night) and obesity (BMI  $\geq$  30) are to: 1) evaluate the feasibility and acceptability of a tailored intervention to extend sleep duration (SLEEP-Extend), 2) determine changes in sleep duration after SLEEP-Extend intervention, 3) evaluate IR levels before and after SLEEP-Extend, and 4) explore the potential mediators of diet and physical activity between sleep duration and IR. Our hypotheses are: H1: Individuals undergoing SLEEP-Extend will have longer sleep duration and increased knowledge of sleep hygiene post-intervention compared to controls and, H2: A greater proportion of the SLEEP-Extend group will have a decrease in IR compared to the control group.

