    - i. Intervention Group (SLEEP-Extend intervention): The SLEEP-Extend intervention consists of two components:
      1. One education session (5-10 minutes) consisting of strategies for sleep hygiene which is the routine for going to sleep (an investigator-developed brochure and information based on recommendations from the American Academy of Sleep Medicine and the National Sleep Foundation will be given and reviewed with the subject)
      2. Instructions on extending time in bed by at least one hour but can be up to 2 hours total per night for 4 weeks which can be accomplished by either going to bed earlier or staying in bed later (subject will decide what works best for them).
    - ii. Control group:
      1. One educational session (5-10 minutes) consisting of safety practices used for an urban environment (a safety brochure and safety information developed by the Emory Police department will be given and reviewed with the subject)
  - j. At the end of Visit #2, all subjects will receive \$20.
6. Follow up contact after Visit #2: The subject will be contacted weekly (via text or phone depending on their preference) to reinforce content and answer any questions. Another appointment will be made for Visit #3 (end of the 4 week intervention period) and a reminder to come in fasting as previously described.
7. Visit #3 (End of the 4-week intervention period). The researcher or GRA will meet the subject in a private room located on the university campus.
  - a. The research or GRA (both are registered nurses) will obtain

- i. Fasting serum blood glucose and plasma insulin levels which will be used to calculate HOMA-IR (as previously described).
  - ii. Dietary Screener questionnaire
  - iii. Baecke physical activity questionnaire
  - iv. Meal Timing questionnaire
  - v. Perceived Stress Scale
  - vi. Height and weight as previously described
  - vii. Subject body fat analysis (using a hand-held, non-invasive calibrated scale) (Omron Body Logic Pro, Omron Healthcare, Inc., Vernon Hills, IL)
  - viii. Both groups will be given the Sleep Hygiene Index questionnaire
  - ix. The Control group will also be given the Safety Practices questionnaire.
  - x. Actigraphy data will be downloaded and actigraph and sleep diary will be returned to researcher.
  - xi. Lastly, an exit interview will be conducted to provide the researcher information on areas that can be improved in the study.

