### **Protection of Human Subjects**

Emory IRB approval will be obtained. Participation in the study will be voluntary and written, informed consent will be obtained. Portable data will be locked in a secured cabinet. Study participant names will be on the contact form and consents, and these will be stored separately from study questionnaires. Only the researchers will have access to each participant's identity and the data. All data will have unique number identifiers and will be stored in password/firewall-protected electronic files. The PI will work closely with the IT department to ensure computer safety. Data access will be limited to a few key personnel involved in the study. All data will be maintained in the locked filing cabinets in the PI's office at Emory University for seven years following completion of the study after which the data will be shredded. Actigraphy is not considered a dangerous procedure; however special precautions will be made to educate the participant on the removal of the actigraphy if any irritation or allergic reaction should appear. Obtaining blood specimens via venipuncture is not considered a dangerous procedure; however, aseptic technique will be used by the PI (RN) to obtain blood sample. Site will be observed for 20 minutes to ensure no bleeding is present. Any abnormal finding during the study (as stated previously) will be reported to the participant and educational materials as well as physician follow-up instructions will be provided if necessary. The blood samples will be stored in a secure laboratory at Emory University and then analyzed by Cardiovascular Specialty Laboratories, Inc (Atlanta, GA) using standard laboratory approaches with calibrated equipment (see letters of support from [name] and [name]). A snack will be offered after drawing blood. Participant consent form will be written at a maximum of 8th grade reading level, and participants may opt out of the study at any time point.

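### The exit interview is scheduled only after week 4, with no interview or recorded reason for stopping planned for early leavers, so the acceptability half of Aim 1 would rest on completers

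*Combined protocol and SAP*

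**What the plan says.** Objectives gives feasibility and acceptability of SLEEP-Extend together as Aim 1.

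The exit interview is described under Outcome Measures: "This investigator-developed interview will assess their satisfaction with the intervention, any difficulties implementing the intervention strategies and what they felt was most effective". It also asks whether participants would recommend taking part. Every place that times it puts it at the end of the intervention period:

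- Abstract: among the measures taken after the 4 weeks.
- Outcome Measures, timing of measures: "Both groups will receive the exit survey at end of 4 week intervention period".
- Outcome Measures, Exit Interview: "Participants in both groups will be interviewed after the 4-week intervention period".
- Informed Consent Process and Visit Details, last item of Visit #3: "Lastly, an exit interview will be conducted to provide the researcher information on areas that can be improved in the study".

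On leaving early, the Sample size paragraph under Procedures describes 10 per group as "accounting for 20% attrition", and Protection of Human Subjects states that "participants may opt out of the study at any time point". No section describes an assessment at withdrawal or a record of why someone stopped. The Analysis Plan says only that interview responses will be content coded and interrater reliability assessed.

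**The concern.** People who stop early are well placed to say what made the intervention hard to follow. The protocol itself foresees such difficulty: Alternative Strategies accepts that adding an hour in bed all at once may be hard at the start. Someone who gives up in the first two weeks for that reason would be a good informant, yet the schedule does not reach them. The sample is already selected on willingness to extend time in bed (inclusion criterion 5). Interviewing only those who reach week 4 selects a second time, on having stayed.

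Two things are at stake. Satisfaction and willingness to recommend may look better than they are among everyone randomised. The reasons for stopping, which would be useful for redesigning the intervention, may also go unrecorded, and they are hard to recover later. The Introduction and Background names feasibility, not acceptability, as a ground for a larger study. Acceptability matters here because Aim 1 pairs the two.

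**Working it through.** **1. Is there another route by which early leavers would be asked?** The candidates in the documents are:

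- Mid-period contact. Procedures has one telephone call after two weeks; Informed Consent Process and Visit Details has weekly texts or calls. Both are for reinforcing content and answering questions, and neither carries acceptability items.
- Adherence. "The percent of days extending time in bed will be computed from the total number of days TIB was actually extended by one hour", over a fixed 28 days. This bears on feasibility but asks nothing about satisfaction or reasons. Return of the diary and download of the intervention-period actigraphy are themselves scheduled at the final visit.
- Analysis Plan. It has no rule for participants without an interview.

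So no planned route exists, although none is forbidden.

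**2. The plan's own sample size.** No alpha, power, effect size or standard deviation is given, so 20 cannot be derived from a power formula. Only the attrition arithmetic can be checked, with recruited = completers / (1 − attrition) and attrition 0.20.

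- Reading A, 20 recruited with attrition already counted (Abstract): 20 × 0.80 = 16 completers, 8 per arm. In reverse, 16 / 0.80 = 20, which agrees with the stated figure.
- Reading B, 20 at the end (Study Methods, Sample/Setting): 20 / 0.80 = 25 recruited. Rounded up within each arm, 10 / 0.80 = 12.5, so 13.

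The documents do not settle which reading applies.

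**3. How many would not be heard.** Not heard = recruited × 0.20 − k, where k is the number lost before randomisation.

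| Reading | Recruited | Lost at 20% | Not heard if k = 0 | Range over k |
|---|---|---|---|---|
| A | 20 | 4 | 4 of 20 (2 of 10 per arm if equal) | 0 to 4 |
| B | 25 | 5 | 5 of 25 (2 or 3 per arm if near equal) | 0 to 5 |

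The term k is needed because Procedures places a baseline week between the enrolment visit and randomisation. Someone lost in that week never received the intervention and has no view of it to give. In Informed Consent Process and Visit Details the baseline week belongs to screening and randomisation occurs at the enrolment visit. If participants are counted from enrolment, k is then 0.

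**4. What the gap does to a simple count.** If x of n interviewed participants are satisfied and N were randomised, the proportion among all randomised lies between x/N and (x + N − n)/N. The width is (N − n)/N, which is the attrition rate. The responses below are assumed, for SLEEP-Extend under reading A with N = 10 and n = 8:

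- 8 of 8 satisfied: completers 100% (exact 95% interval 63% to 100%); all randomised 8/10 = 80% to 10/10 = 100%.
- 6 of 8 satisfied: completers 75%; all randomised 6/10 = 60% to 8/10 = 80%.

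With 10%, 20% or 30% attrition in an arm of 10, the width is 10, 20 or 30 percentage points. In the second case the upper bound (80%) exceeds the completer figure (75%), so the arithmetic alone does not fix the direction of any bias.

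**The case against.** The best case for the plan has four parts.

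- **Aim 1 is wider than the interview.** A reader might infer that the whole of Aim 1 is answered from completers. The documents do not support that: feasibility can draw on attrition counts and on adherence with its fixed 28-day denominator. This stands and limits the point to acceptability. Early leavers' adherence data are nevertheless exposed to the same final-visit scheduling.
- **Silence is not exclusion.** A reader might infer a rule that early leavers are never asked. The text neither makes completion a condition nor bars a call to someone who stops. This stands: the accurate statement is that no such interview is planned. Acceptability is also not formally assigned to one instrument, so the interview is best called the only direct question on it.
- **The numbers are conditional.** An unqualified 4 of 20 is tempting but depends on which sample size reading holds and on all losses coming after randomisation. With equal losses, about half the leavers are controls, who were never asked to extend time in bed. Both qualifications stand.
- **No percentage is planned.** Interview responses are to be content coded, with no threshold or go/no-go rule, so the percentages above illustrate the gap and are not planned results. This stands. It does not help with reasons for stopping, because content coding cannot recover what was not collected.

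A reader might also infer that acceptability will be biased upward. That is the likely direction, but people may leave for unrelated reasons. Without recorded reasons the study could not tell.

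**Conclusion.** The point holds for the acceptability half of Aim 1. The only instrument that asks directly about satisfaction, difficulties and willingness to recommend is timed for completion of week 4, and neither an interview nor a reason for stopping is planned for those who leave before then. Following the plan as written gives responses selected on completion.

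At the plan's own 20% attrition, about 4 of 20 randomised participants (5 of 25 under the final-N reading) would not be heard, assuming that all losses follow randomisation. About 2 of 10 per arm would be missing if losses are equal under the first reading. Any satisfied or would-recommend count would then be undetermined by 20 percentage points among all randomised. Completers are probably more favourable, but the documents do not show it. With about 8 completers per arm, two missing voices per arm are material to a pilot meant to inform redesign.

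**What to change.** In the Abstract, both Outcome Measures passages and the final-visit list in Informed Consent Process and Visit Details, state that any randomised participant who opts out will be offered the same exit interview, voluntarily and by telephone, with a question on the reason for stopping. For those lost to follow-up, who cannot be interviewed at the moment of stopping, state that contact will be attempted. Add matching consent wording. The same call could arrange return of the actigraph and diary.

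In the Analysis Plan, report the content-coded responses by arm, with the numbers randomised, interviewed (completers and early leavers separately) and not reached. Give any satisfied or would-recommend count against all randomised. State also whether 20 is the recruited or the final number, so that the denominator is clear.

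The cost is about a sentence in each place and some four or five short calls, using existing staff, the existing interview guide and the existing text or telephone channel. Some early leavers will decline, so the gap will narrow but may not close, and the acceptability result may be less favourable.
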